7.1 Annual Safety Reporting

The CI/PI will send the Annual Progress Report to the REC using the NRES template (the anniversary date is the date of the REC “favorable opinion letter” and to the Sponsor.

8 Ethical and Regulatory Issues

8.1 Ethics Committee (EC)

The protocol and Patient Information Sheet, informed consent forms will be reviewed and approved by the EC prior to commencing the study. The Ethics Committee written, signed approval letter must contain approval of the designated investigator, the protocol (identifying protocol title and version number) and the patient information and consent.

By signing the protocol, the investigators agree to conduct the study in accordance with the Declaration of Helsinki, Good Clinical Practice and ISO 14155:20011 (1).

8.2 Informed Consent

This will be obtained for each participant prior to initiating any trial procedures (however, interested subjects will be asked if willing to undertake the short questionnaire on initial telephone screening). A copy of the informed consent will be given to the patient and the master copy signed by the subject will be retained in the Investigator File.

8.3 Quality Assurance

Responsibility for accuracy and completeness of the study records and for the data management will lie with the JCRF

8.4 Record Retention

The investigator will maintain confidential all study documentation, and take measures to prevent accidental or premature destruction of these documents.

The documents will be retained in accordance with regulatory guidelines and those of its institution. Records will be stored in the JCRF, prior to off-site storage at a long-term storage facility.

The Investigator will notify the Sponsor prior to destroying any study essential documents following the Clinical Trial completion or discontinuation.

9 General statistical considerations

All baseline, disposition, protocol compliance, exposure and outcome variables (efficacy, safety and exploratory) will be listed and summarized.

The standard summary statistics for continuous baseline and outcome variable are N.mean, standard deviation, median, quartiles, minimum and maximum. The standard summary statistics for categorical baseline and outcome variable are: count and proportion (expressed as percentage).

Sample size calculation

No formal sample size has been calculated for this pilot study.

Endpoints

Primary Efficacy Endpoints

The primary endpoint is the change in IBS severity score from baseline (visit 1) to four weeks (visit 2).

Secondary Efficacy Endpoints

The secondary efficacy endpoints comprise the change in IBS severity score from baseline at two and four weeks will include:

- 1 Severity of abdominal pain
- 2 Frequency of abdominal pain
- 3 Change in abdominal bloating
- 4 Change in bowel habit "satisfaction"
- 5 Change in impact of IBS upon lifestyle
- 6 Change in bowel frequency
- 7 Change in stool consistency
- 8 Change in absence from work days related to IBS (as defined by IBS severity score scales)
- 9 Change in IBS QoL Questionnaire Scores.

Safety Endpoints

The safety endpoints are the incidence, nature, severity, relatedness, duration,

outcome, seriousness and expectedness of treatment emergent adverse events.

Missing Data

Subjects with missing efficacy data will be analysed on a last-observation-carried-forward basis.

8 Study conduct

Any protocol deviations will be categorized as ‘major’ or ‘minor’, listed, and summarized. All subjects will be given a unique patient identifier number at time on consent which will be used to record all data on the CRF and study database. This ensures patient confidentiality and only staff involved in the study will have access to this database. The database will be shared with the study statistician, who will not have any linked patient identifiers.

The sponsor company representative will be given access to relevant patient information for the purpose of study monitoring to ensure the study and subjects have been recruited and managed in accordance with the protocol and REC approval.

9 Efficacy analysis

Summary statistics will be presented for each efficacy endpoint at baseline, two and four and for the change from baseline at two and four weeks.

10 Safety analysis

The incidence, nature, severity, relatedness, duration, outcome, seriousness and expectedness of treatment emergent adverse events will be listed and tabulated. Reporting of events will be as outlined in Appendix 6.

11 Exploratory analysis

This may include but not limited to:

- Analyzing completing subjects only, repeating parametric analyses using non-parametric analyses, analyzing using a longitudinal model, and investigating different methodologies for adjusting for missing values.

12 Funding

The study will be funded by Ateria Health Ltd. As the sponsor, they have confirmed patient indemnity with CAN Insurance Co. Ltd. For £5,000,000.

13 Reporting and Publication

A final report will be completed and either a full report or summary will be submitted to the REC and R&D after perusal and consent from the Sponsor.

It is intended to publish the results whether positive or negative, in both abstracts and major gastroenterological journals.

14 References

1. Forbes AL Hunter J O Irritable Bowel Syndrome *Medicine* 35 267-271 2007
3. Editorial: balancing fibre and FODMAPs in IBS - a 'rye' look at an old problem. Quigley EM. *Aliment Pharmacol Ther.* 2016 Nov;44(10):1134-1135. doi: 10.1111/apt.13805.

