3. A urine sample will be collected at baseline and frozen to be sent to [name], Brunel University Uxbridge for determination of bacterial metabolites by SIFT/MS (specific ion flow tube mass spectrometry). A faecal sample will also be collected and stored prior to sending to Microba in Brisbane, Australia and again at week 4 for microbial analysis.
4. ERME (labelled as JUVIA) a total of 40mls daily (to be taken with meals) Subjects will be supplied with 3 x 450ml containers of JUVIA. Muntons Maltsters of Stowmarket Suffolk will supply the product to our current packers Chyialis Creation house [name]. On receipt of the product from the supplier details will be entered onto an accountability log at JCRF, and stored appropriately. The product will be stored by the research team in a cool (<25 degrees C), dry and secure environment.
5. The participants will be given enough product (JUVIA) to last for 4 weeks and instructed how to take the product with food daily (20mls at breakfast and 20mls with last meal of the day).
6. Patients will be provided with information as to how to store the product at home and asked to contact the team if they have any concerns.
7. Participants will be asked to complete the IBS severity score questionnaire and IBS Quality of Life Questionnaire at 2 weeks and 4 weeks post their first research hospital appointment. A member of the research team will telephone the patient to remind them to do this and, if preferred, can complete the 2-week questionnaires with the patient over the telephone. Week 4 will be undertaken when they attend the final clinic visit.
8. Patients will be made aware that due to the effects of JUVIA, they may

experience bacterial 'die-offs' when essential nutrients for these bacteria are no longer available in the gut, where symptoms are exacerbated during the first few days and encouraged to continue as symptoms will settle.

9. At 4 weeks post Visit 1, a final hospital (Visit 2) will take place and the same procedures undertaken at Visit 1 will be repeated. A further faecal and urine sample will be collected and urine again frozen prior to transporting to the laboratory for analysis.
10. IBS severity score, IBS QoL questionnaires, Nijmegen and will again be completed at week 4 and the patient will be weighed.

4 Adverse Events and Patient withdrawal

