1. It is unlikely that malt extract, which is already widely used in the food industry, will cause any major difficulties or unwanted effects. In the unlikely event that the patient becomes ill while participating in the study they must report this to the Research team at JCRF, Swansea Bay University Health Board who will discuss with the Chief Investigator/Principal investigator whether or not the participant should be withdrawn from the study.

Adverse events will be collected by asking patients about their symptoms during enrolment in the study. The adverse event will be recorded and reported following the Sponsor's normal procedures.

In the event of a Serious Adverse Event in a patient taking part in the study, the Sponsor's normal reporting procedures apply.

Should the participant find the product unpalatable or unacceptable, they will be asked to remain in study follow-up if they are prepared to do so. If a patient stops taking the product then this must be recorded, along with the reason why. Where patients are agreeable the research team will follow up with them 2 weeks after stopping the product and patients will be asked for permission to use the data and samples already collected to that point, together with any subsequent follow-up data.

If the participants wish to withdraw at any point during the study for whatever reason, they will be asked to remain in follow-up and to allow any data and/or samples collected to that point to be included in the analysis. Participants are free to withdraw without prejudicing their future care and details of withdrawal will document in the Case Record Form.

5 Treatment preparations

ERME (Enzyme rich malt extract) – JUVIA – marketed food supplement. 450mls per bottle

40 mls daily JUVIA provided by Muntons, maltsters of Stowmarket and repacked by Chrysalis. Each subject will be given 2 bottles of JUVIA.

6 Samples

Stool Analysis plan

Faecal samples will be stored before being sent as a batch to Microba Brisbane,

Australia for genomic assay using the Shotgun technique for analysis of the microbiome and comparison with their extensive data collection. Microba have developed and validated a method of faecal sampling which involves taking a smear from lavatory paper and storing it in a specially developed container. Full chain of custody will be maintained.

Urine sample

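### Exposure is promised as a reported variable, but the described procedures capture only complete stopping, so partial or missed intake of the 40 ml daily product goes unmeasured

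*Protocol*

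**What the plan says.** The commitment is in the Protocol under General statistical considerations: "All baseline, disposition, protocol compliance, exposure and outcome variables (efficacy, safety and exploratory) will be listed and summarized". Exposure is named there separately from protocol compliance.

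The procedures that bear on intake are these:

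- **Regimen (section 3, items 4 and 5).** The total is 40 ml a day, split as "20mls at breakfast and 20mls with last meal of the day". On quantity, item 5 says "The participants will be given enough product (JUVIA) to last for 4 weeks".
- **Supply.** Section 3, item 4 says "Subjects will be supplied with 3 x 450ml containers of JUVIA". Section 5 (Treatment preparations) gives each subject two bottles of 450 ml.
- **Product log (section 3, item 4).** "On receipt of the product from the supplier details will be entered onto an accountability log at JCRF, and stored appropriately". No entry per subject for product dispensed or returned is described.
- **Week-2 contact (section 3, item 7).** A telephone reminder to complete the severity and quality-of-life questionnaires, which may be completed during the call.
- **Week-4 contact (section 3, items 9 and 10).** "a final hospital (Visit 2) will take place and the same procedures undertaken at Visit 1 will be repeated", with further samples, questionnaires and body weight.
- **Stopping (section 4).** "If a patient stops taking the product then this must be recorded, along with the reason why".
- **Deviations (Study conduct).** Deviations are graded major or minor, listed and summarised. No level of intake is named as a deviation.

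**The concern.** A statistical analysis plan can define how exposure is derived, but it cannot summarise data that no contact collects. If intake is to be reported, the measurement has to be among the study procedures, and none is described there.

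The Protocol itself foresees reasons for taking less than the full amount. It offers a taste test before enrolment, makes provision for subjects who dislike the product, and warns that symptoms may worsen in the first few days. Because the daily amount comes in two portions, dropping one is an obvious way to cut down without stopping.

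The study has no control arm and aims for at least 20 completers. If the severity score changes little, one natural question is whether subjects took the product as planned. With stopping as the only record, that question could not be examined. The exploratory analysis of completing subjects has the same limit, since completing follow-up and taking the product as instructed would look alike. Dosing deviations could be graded only where they happened to come to light.

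**Working it through.** The Protocol gives no figure for exposure to reproduce, so the check has two parts.

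**1. Does any described procedure yield the amount taken?**

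- Product log: described at receipt from the supplier. It gives site stock, not a subject's intake.
- Week-2 call: questionnaires only, with no intake question stated.
- Visit 2: repeats Visit 1. Visit 1 precedes dosing, so repeating its procedures cannot measure intake. The stated additions are samples, questionnaires and weight.
- Reproduced questionnaires (Rome IV, malfermentation, severity score, IBS-QOL, Nijmegen): none asks about product taken.
- Stopping: the fact and the reason are recorded. A date is not expressly required, and reduced or missed portions are not mentioned.

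Only complete stopping is captured.

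**2. Could the amount dispensed stand in for the amount taken?**

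Inputs: 40 ml a day in two portions of 20 ml (section 3, items 4 and 5); 4 weeks, taken as 28 days; 450 ml per container; three containers (section 3, item 4) or two (section 5).

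- Planned volume: 40 × 28 = 1120 ml.
- Every evening portion skipped: 20 × 28 = 560 ml, and 560 / 1120 = 50%.

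| | Three containers | Two bottles |
|---|---|---|
| Supplied | 3 × 450 = 1350 ml | 2 × 450 = 900 ml |
| Against plan | 1350 − 1120 = 230 ml over | 1120 − 900 = 220 ml short |
| Supplied / planned | 1350 / 1120 = 120.5% | 900 / 1120 = 80.4% |
| Days at 40 ml | 1350 / 40 = 33.75 | 900 / 40 = 22.5 |
| Remainder at full use, day 28 | 230 ml | 0 ml (empty from day 22.5) |
| Remainder at half use, day 28 | 1350 − 560 = 790 ml | 900 − 560 = 340 ml |

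The dispensed amount sets only a ceiling on intake, and that ceiling is 120.5% or 80.4% of plan depending on the section. The returned amount is informative. With three containers, full and half use differ by 790 − 230 = 560 ml at Visit 2. With two bottles the 28-day average cannot exceed 900 / 28 = 32.1 ml a day. Empty bottles then mean 900 ml used, whether at 40 ml a day until they ran out or at a steady 32.1 ml a day.

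The first-dose date also matters: each day of error in the denominator is 40 ml, or 40 / 1120 = 3.6% of the planned volume.

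**The case against.** The strongest reply is that the Protocol does produce data under both promised terms. Protocol compliance reads naturally as adherence to the Protocol, which the listing of major and minor deviations covers. Exposure can be summarised as continuing or stopped, with reasons. The case record form is cited but not reproduced and may hold an intake item. The efficacy analysis is descriptive and makes no dose-response claim, and the Protocol gives no rate of partial dosing. In about 20 uncontrolled subjects, intake and response would be confounded anyway, since subjects who feel worse may take less.

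Much of this stands, and it rules out several stronger readings that a reader might infer:

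- *That no compliance or exposure data exist.* Deviations and stops are recorded; the gap is in partial intake.
- *That the 4-week change cannot be linked to the product at all.* It can be described for subjects assigned 40 ml daily.
- *That the pilot gives no information on acceptability.* Stops with reasons and adverse events give some.
- *That partial dosing is likely.* The documents show that it is foreseeable, not how often it occurs. The taste test and the advice to continue through early worsening are there to reduce it.

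The reply does not close the remaining gap. Exposure is promised as its own variable, and the Protocol mentions no intake item on any form. Confounding limits what an intake figure can prove, but it does not make an unrecorded figure reportable.

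**Conclusion.** The point holds in a limited form. The Protocol promises an exposure summary, while its described procedures support only a table of stopped or not stopped. A subject taking 560 of 1120 ml would be recorded like one taking all of it. The primary endpoint remains valid as a description of subjects assigned the product; what is lost is the ability to set a small change beside the amount actually taken.

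This rests on two assumptions: that 4 weeks means 28 days, and that no form outside the Protocol already collects intake. The 50% case illustrates what would go unseen and is not an estimate. The conflict over supply is a separate contradiction, but it bears on the remedy because any measure based on returned product depends on what was dispensed. The change should be made before subjects are dosed, since unrecorded intake cannot be reliably reconstructed.

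**What to change.** 1. Reconcile the supply statements in section 3 (item 4) and section 5 with each other and with the 1120 ml that 28 days at the stated daily amount requires. Until this is done, a 900 ml supply would hold a subject who follows the instructions to 80.4% on the 28-day measure.
2. In section 3, items 7 and 9, record the first-dose date and the amount dispensed to each subject. Have subjects bring all containers, used and unused, to Visit 2 and record the remainder. Ask about missed or reduced portions at the week-2 call and at Visit 2. Record the date of any stop.
3. Under General statistical considerations, define exposure as (dispensed − returned) / (40 ml × days from first dose to Visit 2), supported by the reported missed portions. Show it descriptively beside the primary change, without reading it as a dose-response result.

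The cost is a wording change, a few extra case record form fields, a few minutes at contacts that already take place, and subjects carrying containers back. The measure will be somewhat imprecise: residue left in containers affects the returned volume, and spilled, discarded or unreturned product counts as taken. The missed-portion question is a partial check on this.

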Appendix 3: completed at clinic visit 1,2 weeks, 4 weeks

IB patient severity score completed 3 times during the course of the study

IBS QUESTIONNAIRE

Name: _____ G.P. Name: _____
 Address: _____ Address: _____
 Telephone: _____ Telephone: _____
 Date of birth: _____

Marital status: Single / Married / Divorced / Widowed / Co-Habit
 Occupation: _____ Sex: M F

Ethnic background: Caucasian (white) / Afro-Caribbean / Asian / Oriental
 Fathers Occupation (even if retired): _____

INSTRUCTIONS

This form is designed to enable us to record and monitor the severity of your IBS. It is to be expected that your symptoms might vary over time, so please try and answer the questions based on how you currently feel (ie over the last 10 days or so). All information will be kept in **strict** confidence.

- For questions where a number of different responses are a possibility please circle the response appropriate to you.
- Some questions will require you to write in an appropriate response.
- Some questions require you to put a cross on a line which enables us to judge the severity of a particular problem.

For example:

How severe was your pain?

Please place your cross (X) anywhere on the line between 0-100% in order to indicate as accurately as possible the severity of your symptom.
 This example shows a severity of approximately 90%.

1

PART 1 : SEVERITY SCORE

- Do you currently suffer from abdominal (tummy) pain? YES NO
Circle appropriate box
 - If yes, how severe is your abdominal (tummy) pain?
 - Please enter the number of days that you get the pain in every 10 days.
 For example if you enter 4 it means that you get pain 4 out of 10 days. If you get pain every day enter 10
 Number of days with pain x10
- Do you currently suffer from abdominal distension* (bloating, swollen or tight tummy) YES NO
(*women, please ignore distension related to your periods) Circle appropriate box
 - If yes, how severe is your abdominal distension/tightness
- How satisfied are you with your bowel habit?
- Please indicate with a cross on the line below how much your Irritable Bowel Syndrome is affecting or interfering with your life in general

IBS SEVERITY SCORE:

2

For office use only
SCORE

IB patient severity score completed 3 times during the course of the study

PART 2 : OTHER IBS DATA

BOWEL HABIT

5. a) What is the most number of times you open your bowels per day/week/month?

Number of times per day / week / month (Circle appropriate)

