Note: For some people the answer to part a and b could be the same

b) What is the least number of times you open your bowels per day/week/month?

Number of times per day / week / month (Circle appropriate)

6. In the following questions you may circle more than one answer:

Are your motions ever:

- a) normal often / occasionally / never (Circle appropriate)
- b) hard often / occasionally / never (Circle appropriate)
- c) very thin (like string) often / occasionally / never (Circle appropriate)
- d) in small pieces (like rabbit pellets) often / occasionally / never (Circle appropriate)
- e) mushy (like porridge) often / occasionally / never (Circle appropriate)
- f) watery often / occasionally / never (Circle appropriate)

7. In the following questions you may circle more than one answer:

[figure not shown]
Do you ever:

- a) pass mucus (or slime or jelly) with your motions YES NO Circle appropriate box
- b) pass blood with your motions YES NO
- c) have to hurry/rush to the toilet to open your bowels YES NO
- d) strain to open your bowels YES NO
- e) feel you haven't emptied your bowel completely after you have passed a motion YES NO

PART 2 : Continued

SITE OF PAIN

Please mark with a cross (x) on the diagram below where you get your pain (use more than one x if necessary)

8. Do you ever:

- a) notice your stools are more frequent or loose when you get pain YES NO Circle appropriate box
- b) notice whether the pain is frequently eased by opening your bowels YES NO Circle appropriate box

9. In the last year on approximately how many weeks were you:

- i) absent from work due to IBS (enter 52 if you have given up completely work because of IBS) -----
- ii) at work suffering from IBS -----

Appendix 4

IBS-QOL – questions (need approval to download actual questionnaire)

Completed at screening / week 2 / week 4

Life Measure (IBS-QOL)

The IBS-QOL consists of 34 items, each with a five-point response scale:

Items 1, 2, 4, 8-10, 12, 13, 16, 25-29, 34

1. Not at all 2. Slightly 3. Moderately 4. Quite a bit 5. Extremely

Items 3, 5-7, 11, 14, 15, 17-24, 30-33

1. Not at all 2. Slightly 3. Moderately 4. Quite a bit 5. A great deal

1. I feel helpless because of my bowel problems.
2. I am embarrassed by the smell caused by my bowel problems
3. I am bothered by how much time I spend on the toilet.
4. I feel vulnerable to other illnesses because of my bowel problems.
5. I feel fat because of my bowel problems.

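### Secondary endpoint 8 (change in work-absence days at 2 and 4 weeks) rests on a question about weeks absent in the last year, so the change cannot be interpreted as a product effect

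*Protocol*

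**What the plan says.** Protocol section 9, General statistical considerations, introduces the secondary endpoints with "The secondary efficacy endpoints comprise the change in IBS severity score from baseline at two and four weeks will include". Item 8 of that list is "Change in absence from work days related to IBS (as defined by IBS severity score scales". The later section on efficacy analysis commits to reporting it: "Summary statistics will be presented for each efficacy endpoint at baseline, two and four and for the change from baseline at two and four weeks".

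The form in question is Appendix 3, given three times: "Appendix 3: completed at clinic visit 1,2 weeks, 4 weeks". Its general instruction is to "answer the questions based on how you currently feel (ie over the last 10 days or so". Part 1 produces the severity score. Absence is asked about only in Part 2, headed "PART 2 : OTHER IBS DATA", at question 9, which begins "In the last year on approximately how many weeks were you" and continues at sub-item i with "absent from work due to IBS (enter 52 if you have given up completely work because of IBS". Sub-item ii concerns weeks at work while suffering from IBS, not absence. No other instrument reproduced in the protocol asks about days or weeks off work.

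**The concern.** The endpoint and its source differ in three ways.

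- **Unit.** The endpoint is in days. The item is in approximate weeks.
- **Recall period.** The endpoint is a change over 2 and 4 weeks. The item looks back a full year each time it is asked, so baseline and follow-up answers describe almost the same period.
- **Location.** The endpoint is said to be defined by the severity score scales. The item lies in Part 2, outside the scored Part 1.

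At stake is whether the tabulated change says anything about the product. Followed as written, the plan yields a figure that a reader could take as evidence for or against an effect on work absence when it supports neither.

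**Working it through.** The plan gives no figure to reproduce for this endpoint, and none is needed: the check is arithmetic on the recall window.

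**Inputs from the protocol.** Window of question 9: one year, taken as 52 weeks (the form itself uses 52 as its full-year code). Follow-up times: w = 2 and w = 4 weeks. Treatment lasts 4 weeks (section 3).

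**Assumption.** The protocol gives no level of absence, so I take A = 2, 4 or 8 weeks per year as an illustrative range.

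**Step 1: overlap with the baseline window,** (52 − w)/52.
- Week 2: 50/52 = 96.2%; new share 2/52 = 3.8%.
- Week 4: 48/52 = 92.3%; new share 4/52 = 7.7%.

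**Step 2: what the change measures.** With accurate recall, the shared weeks cancel:

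change = (absence in the w new weeks) − (absence in the w weeks that leave the window).

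The weeks that leave lie about a year before. They are not recent pre-treatment weeks, so the comparator is wrong for a before-and-after contrast.

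**Step 3: expected change if prior absence was evenly spread and stopped completely on day 1,** −A × w/52.

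| A (weeks/year) | Week 2 | Week 4 |
|---|---|---|
| 2 | −0.08 | −0.15 |
| 4 | −0.15 | −0.31 |
| 8 | −0.31 | −0.62 |

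For an expected fall of one whole week, A must be at least 52/w: 26 weeks per year at week 2, or 13 at week 4, even with absence abolished.

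**Step 4: chance of no change at all.** Treat prior weeks as independent, each with absence probability A/52, and absence as abolished on product. The probability of exactly zero change is (1 − A/52)^w. For A = 4 this is (48/52)² = 0.85 at week 2 and (48/52)⁴ = 0.73 at week 4.

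**Step 5: uneven absence.** Suppose a subject's only absence was 4 weeks, all within the 4 weeks that leave the window by week 4, with none on product. The change is 0 − 4 = −4 weeks, although recent pre-treatment absence was already nil. The figures in Step 3 are thus expectations under even spread, not bounds.

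**Step 6: the code 52.** A subject who has given up work is told to enter 52. That answer stays at 52 unless the subject resumes work within the 4 weeks; even then a literal count could fall only to 52 − 4 = 48.

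**The case against.** The form tells patients to answer for about the last 10 days, which might seem to give question 9 a short window. It does not: that instruction concerns how the patient currently feels, and question 9 states its own one-year period. Nor could a separate analysis plan repair this, because short-term absence cannot be recovered from a one-year count.

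Other objections do stand, and they limit the point.

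- A reader might infer that the endpoint cannot register any effect. The arithmetic does not support that: 2 or 4 on-product weeks do enter the window, and a heavily absent subject could show a shift.
- A reader might infer that the mean change will lie near zero. The protocol gives no baseline absence, spread or reliability for the item. No control arm or blinding is described, so repeated recall could drift in one direction.
- A reader might infer that the result would be published as no effect on absence. The protocol commits only to summary statistics and to publishing whatever the outcome. No test or success rule is attached to endpoint 8, so misreading is a possibility, not a prediction.
- The consequence is small: one of nine secondary items in a pilot without a formal sample size. The primary endpoint does not use question 9.

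**Conclusion.** The point holds in limited form. Endpoint 8 and its only source disagree on unit and recall period, and the resulting change is uninterpretable as a product effect: the windows overlap by 96% and 92%, and the comparator is absence about a year earlier. The overlap figures need only the one-year window and the visit times. The expected falls of 3.8% and 7.7% also assume evenly spread prior absence that ceases on day 1; the falls in weeks rest further on the assumed 2 to 8 weeks per year, and the zero-change probabilities on independence between weeks. Subjects coded 52 have little scope to change in four weeks. The primary and other secondary endpoints are unaffected. The correction should be made, but it does not threaten the main result.

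**What to change.** Either of two changes resolves it.

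1. **Simplest.** Keep question 9 as a baseline descriptor and delete endpoint 8 as a change endpoint. This is a wording change only; the cost is that the trial then reports nothing on change in work absence.
2. **To keep the endpoint.** Add one item at Visit 1, week 2 and week 4 asking for the number of days absent from work because of IBS over a short recall period no longer than the assessment interval, for example the last 14 days. Define endpoint 8 as the change in that count, and report how many subjects are in work at each assessment.

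The second option costs one question on three existing forms. Its drawbacks are that the item is not part of the original questionnaire and that many counts may be zero in a sample of 20 to 30, so it should be reported descriptively.
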